7.5.4 HAMA Testing

Serum from blood drawn for functional studies at baseline and at week 6 will be stored for measurement of HAMA. These studies will be performed in the event of a suspected immunologic reaction.

7.5.6 Sample Collection Requirements if CRS or Severe Toxicity Occurs

A serum sample (~1 mL) for IL-6 analysis and ~20 mL of blood should be collected from any subject who develops signs and symptoms of CRS. This sample should be collected before treatments are administered to alleviate CRS symptoms. Subsequent 20 mL blood samples should be collected once a day for the first 3 days. At the discretion of the sponsor, a daily sample may be requested for an additional 4 days.

In addition, a serum sample, (\sim 1 mL) for IL-6 analysis and \sim 20 mL of blood should be collected in any subject who develops a SAE (i.e., requiring hospitalization) related to the cell infusion. Subsequent 20 mL blood samples should be collected once a day for the first 3 days. At the discretion of the sponsor, a daily sample may be requested for an additional 4 days.

An additional blood sample of approximately 20 mL may be collected if any subject develops an AE or event of clinical significance that is thought to be at least possibly related to the CAR T cells.

7.5.7 Other Tissue Studies

If biopsy of accessible lymph nodes or other tissue is required at any time after treatment, a sample of this will be used to assess presence of transduced peripheral blood T-cells in association with the tumor. Additionally, this tissue may be used to assess for potential causes for loss of response to therapy, including, but not limited to, the loss of CD30 expression.

If bone marrow trephine biopsy or tumor biopsy is required at any time after treatment, a sample of this will be used to assess presence of transduced peripheral blood T-cells in association with the tumor. Additionally, this tissue may be used to assess for potential causes for loss of response to therapy, including, but not limited to, the loss of CD30 expression.

If the subject dies, an autopsy may be requested. If an autopsy is granted, tissue may be requested to assess presence of transduced cells. Additionally, the autopsy tissue may be used to assess for potential causes for loss of response to therapy, including, but not limited to, the loss of CD30 expression.

7.5.8 Biobank Repository

Subjects participating in this trial will be asked to consent to allow researchers to store their biological specimens. Participants in this trial will also be required to sign a separate HIPAA authorization form to allow investigators to review their medical records.

ATLCAR.CD30 cells will be stored at the GMP facility according to standard procedures. Other specimens collected during this study as described in section 7.5.7 of this protocol will be stored at the University of North Carolina at Chapel Hill in the immunotherapy laboratory in locked liquid nitrogen tanks with controlled access. The samples will be labeled with the study ID number and date and time of sample collection.

The purpose of this repository or biobank is to store samples for immediate or future analyses to answer study-related questions, not to increase general knowledge outside the parameters of the study. These goals will be accomplished using several different kinds of specimens collected during the study as described. These specimens include:

- Tissue samples from standard of care biopsies of the bone marrow, lymph nodes and/or extramedullary tumor
- Unused ATLCAR.CD30 cells after a determination has been made that the subject is not a candidate for re-infusion or has already undergone re-infusion.

- Unused additional material collected during procurement (peripheral blood mononuclear cells)
- Leftover tissue obtained for any standard of care procedure that may provide additional information about ATLCAR.CD30 cell therapy.

For example, analyses will be performed to assist in determining if the ATLCAR.CD30 cells are associated with the tumor and if the ATLCAR.CD30 cells are present.

Tissues donated from bone marrow biopsies, lymph nodes, extramedullary tumor biopsies, or any leftover tissue obtained through standard of care procedures that may provide additional information about ATLCAR.CD30 cell therapy will be stored for 15 years in the repository. After 15 years, these samples will be destroyed. ATLCAR.CD30 cells will be kept for 5 years and destroyed thereafter.

Information about the patient's disease will be linked to the specimens stored in the repository database. Immunotherapy laboratory-associated research staff, LCCC Bioinformatics staff who support the database and the LCCC Data Warehouse, and researchers with IRB-approval for access to personal health information for each subject in this study will be able to link specimens to relevant medical information. Some results from laboratory analyses that occurred during the patient's participation in the clinical study may also be included. This information may be important for understanding how the patient's cancer developed and responded to treatment.

Storage Time:

- CAR-T cells and material from procurement are to be stored for up to 15 years for subject treatment and safety purposes. If storage of the CAR-T cells and/or extra material from procurement is no longer deemed necessary as determined by the Principal Investigator with appropriate consult, as needed (e.g., attending physician, treating physicians, etc.), the CAR-T cells and/or the extra material from procurement may be released for archiving or destruction earlier than 15 years. At the time of release determination by the Principal Investigator, if the subject did not consent for their specimens to be used for further research or quality assurance/quality control (QA/QC) activities, the specimens will be destroyed. The subject may withdraw their consent at any time to prevent the use of their specimens for further research or QA/QC activities. Withdrawing of consent will result in the destruction of the samples at 15 years or at the time consent is withdrawn if this occurs after the initial 15 years in storage.
 - Archived samples will be stored in the GMP lab (the ACT facility) and will be designated in the inventory system for use in laboratory research and/or QA/QC activities. Samples will be de-identified when they are used for

laboratory research or QA/QC activities. Total storage time (initial storage and archiving) may be up to 25 years, and then the samples will be destroyed.

• Tissue obtained from bone marrow biopsies, extramedullary tumor biopsies, or any leftover tissue obtained through standard of care procedure or as outlined as part of the protocol that may provide additional information about ATLCAR.CD30 cell therapy will be stored for up to 15 years.

Provision of Data to Correlative Scientists

Identification and Role of the Study Coordinator as the Honest Broker

The study coordinator will be in charge of collecting and maintaining all data points and data management. The study coordinator should have adequate training to enter, manage, and deidentify data. The study coordinator will provide a unique study number to each enrolled subject. All documentation and samples will be labeled with the unique study number. The correlative teams will only be provided this unique study ID number as opposed to any other patient identifiers. The clinical team will be the only people able to access identifiable data and the study coordinator will be a conduit to provide the de-identified data to the correlative team.

Requests for a data

Identifiable data will not be given out to any correlative investigators at any time. Multicenter and UNC correlative Investigators may ask the study coordinator for a specific data set, and the study coordinator will return a deidentified data set. This data may only be used for purposes of the study. Any use other than directly related to the study must be approved by the IRB of record. If there is a need for an investigator to access identifiable data during the study, then a new IRB application will need to be submitted from that investigator detailing the reasons needed to access that data. The study coordinator will also ensure that correlative results are not returned from the correlative team to the clinical team to dictate treatment or follow-up decisions unless this is specifically approved by the IRB of record and delineated in the clinical protocol.

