7.4 Long Term Follow-Up

Quantitative real-time PCR to detect transgene copy numbers will be collected preinfusion, 3-4 hours post infusion, 1, 2, 3, 4 and 6 weeks post- T cell infusion, 3, 6, 9, and 12 months post- T cell infusion and then yearly for a total of 15 years. If transgene copy number is >1000 copies/1µg DNA, then samples to determine transgene copy numbers will be collected every 6 months after the first year until transgene copy number is <1000 copies/1µg DNA at which time samples will then be collected yearly for a total of 15 years.

If at 6 months post- T cell infusion, transgene is detected at >0.5% by flow cytometry then PCR to detect retroviral integrant clonality and integrant locus will be performed and will continue every 6 months until detection is <0.5%. Samples will then be collected annually and may be archived for a total of 15 years. If the level of detection is less than 0.5%, samples will be collected annually and may be archived. Follow up will continue for 15 years.

If a subject develops a delayed adverse event that is related to the trial drug, then more frequent (2-4 times per year) clinical observation may be indicated. Appropriate follow up will be conducted based on a particular subject's prior test results. The investigator will determine the additional testing and sample collection that is needed. New malignancies and delayed adverse events will be recorded during long term follow-up.

Regarding annual genetic analysis through year 15, see Section 7.5.5.

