7.5 Correlative Studies: Tests of Function, Persistence and Safety

The following investigations will be used to monitor function and persistence in peripheral blood and safety of transduced T-cells at time-points indicated in the Time and Events Table. A maximum of the lesser of 50 mL or 2 mL/kg of body weight of blood will be drawn on any one day for these assays. If a subject's hemoglobin is less than 8.0 g/dL at any of the evaluation times, the amount of blood drawn for the evaluation will be reduced and may be obtained over more than one venipuncture, if necessary. If there is insufficient blood, samples archived for RCR testing if needed, and Quantitative real-time PCR, will be the first priorities. Note: the studies are not necessarily performed at the time of blood collection. Correlative blood sample collection will cease if the samples are no longer required for persistence and function or clonality analysis.

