7.5.3 Clonality

If the transgene is detected at > 0.5% by either flow cytometry (if feasible) or by qPCR at the 6-month sample collection timepoint, then PCR to detect retroviral integrant clonality and integrant locus will be performed. This analysis will continue every 6 months until detection is < 0.5% for up to 5 years. After this time, it will be collected

annually. If the level of detection is < 0.5% at 6-months, samples will be collected annually and may be archived. Samples will no longer be collected if detection is < 0.5% for more than 1 consecutive testing period.

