10.4 Data and Safety Monitoring Plan

The Principal Investigator will provide continuous monitoring of subject safety in this trial with periodic reporting to the Data and Safety Monitoring Committee (DSMC). [name] will discuss any DLT event as it occurs, and in consultation with the study statistician, make a decision regarding continued accrual and dose escalation as appropriate. In addition, this triad will evaluate any unexpected toxicities as they occur, and determine if any changes to toxicity monitoring are required.

Meetings/teleconferences will be held with the team at a frequency dependent on study accrual, and in consultation with the study Biostatistician. These meetings will include the investigators as well as study coordinators, data coordinators, regulatory associates, clinical data management associates, and any other relevant personnel the principal investigators may deem appropriate. At these meetings, the research team will discuss all issues relevant to study progress, including enrollment, safety, regulatory, data collection, etc.

The team will produce summaries or minutes of these meetings. These summaries will be available for inspection when requested by any of the regulatory bodies charged with the safety of human subjects and the integrity of data including, but not limited to, the oversight (Office of Human Research Ethics (OHRE) Biomedical IRB, the Oncology Protocol Review Committee (PRC) or the North Carolina TraCS Institute Data and Safety Monitoring Board (DSMB)).

The UNC LCCC Data and Safety Monitoring Committee (DSMC) will review the study on a regular (quarterly to annually) basis, with the frequency of review based on risk and complexity as determined by the UNC Protocol Review Committee. The UNC PI will be responsible for submitting the following information for review: 1) safety and accrual data including the number of subjects treated; 2) significant developments reported in the literature that may affect the safety of participants or the ethics of the study; 3) preliminary response data; and 4) summaries of team meetings that have occurred since the last report. Findings of the DSMC review will be disseminated by memo to the UNC PI, PRC, and the UNC IRB and DSMB.

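### Section 7.5.8 restricts the return of correlative results, and the protocol gives a dominant clone found by scheduled clonality PCR in a well subject no stated route to the investigator

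*Combined protocol and SAP*

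**What the plan says.** Section 7.5 groups RCR testing, clonality and human anti-mouse antibody (HAMA) testing under correlative studies and gives their purpose: "The following investigations will be used to monitor function and persistence in peripheral blood and safety of transduced T-cells".

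Section 7.5.3 makes clonality testing conditional on transgene level alone. If the level exceeds 0.5% at the 6-month sample, "then PCR to detect retroviral integrant clonality and integrant locus will be performed". Testing repeats every 6 months while the level stays above that threshold, for up to 5 years, with annual collection afterwards. Sampling ends once the level has been below 0.5% for more than one consecutive testing period.

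Section 7.5.8, in its text on the honest broker, states that "the study coordinator will be a conduit to provide the de-identified data to the correlative team". It then makes the coordinator responsible for ensuring that "correlative results are not returned from the correlative team to the clinical team to dictate treatment or follow-up decisions unless this is specifically approved". The full exception reads "unless this is specifically approved by the IRB of record and delineated in the clinical protocol", so both conditions must be met.

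Section 7.4, on long-term follow-up, says "Appropriate follow up will be conducted based on a particular subject's prior test results". That sentence stands in a paragraph about subjects who have developed a delayed adverse event related to the product.

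Section 10.4 lists what the Principal Investigator sends to the DSMC. It begins with "1) safety and accrual data including the number of subjects treated" and continues with literature developments, preliminary response data and team-meeting summaries.

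**The concern.** Section 8.3 accepts that the vector could integrate at a site that leads to leukemia, although it judges the risk small. Clonality and integrant-locus PCR is the scheduled test that bears on that risk. A safety test protects a subject only if someone who can act on it receives the result and may use it. Here a general rule on correlative results meets a safety assay that the protocol itself labels correlative, and no sentence exempts that assay.

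The subject most exposed is one who feels well. In the Time and Events Table, the blood count is scheduled only to month 12, and footnote 1 ends the required annual physical exam after 5 years. Yearly history continues and asks about new malignancies and hematologic disorders, but it picks these up once they have appeared. A clonality result could be the earlier sign.

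**Working it through.** There is no figure to reproduce. The check sets the passages side by side.

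1. **Is clonality a correlative result?** Yes. Section 7.5.3 sits under section 7.5, and footnote 11 of the Time and Events Table lists clonality as item b of the correlative analyses. Appendix IV does the same for subjects on alternative therapy.

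2. **What does section 7.5.8 restrict?** It restricts return to the clinical team for one purpose, steering treatment or follow-up. The only data flow it describes runs from the clinical side to the laboratory; no reverse flow is set out.

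3. **Does the exception cover clonality?** It needs IRB approval and a description in the protocol. Sections 7.4 and 7.5.3, footnote 11b and Appendix IV describe when to sample, how often and when to stop, all by transgene level. They differ on the detection method: flow cytometry or qPCR in 7.5.3 and footnote 11b, flow cytometry only in 7.4 and Appendix IV. None of them defines an abnormal clonal pattern, names a recipient or describes any use of the pattern. The described use is of the transgene level, not of the clonality result.

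4. **Is there another route to the investigator?** Section 7.4 and footnote 17 let the investigator determine additional testing, and base follow-up on earlier results, once a delayed adverse event related to the product has occurred. A well subject does not meet that condition.

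5. **Is there a route to the sponsor or DSMC?** Section 10.3.3 obliges the sponsor to report in vitro findings that suggest significant human risk, but gives no step from laboratory to sponsor. The DSMC list in section 10.4 is broad enough to hold such a result but does not name it. Sections 11.3.1 and 11.3.2 (safety analyses) do not include clonality. Section 11.3.5 treats integration location only in relation to cell behavior.

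6. **Which assays are run in a well subject?**
   - Clonality: yes, on schedule, if transgene exceeds 0.5% at month 6.
   - RCR: no. Section 7.5.2 has samples analyzed only after one of five listed clinical events.
   - HAMA: no. Section 7.5.4 says "These studies will be performed in the event of a suspected immunologic reaction". It measures anti-mouse antibodies and is not a test of vector integration.
   - Genetic analysis (7.5.5): optional, with the stated aim of relating integration location to cell behavior. Its integration-site findings could overlap with clonality.

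The gap is therefore specific to clonality and integrant locus, with section 7.5.5 as a possible second source of the same information.

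**The case against.** The other side has several fair points.

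- **Purpose.** A reader might infer that section 7.5.8 keeps all correlative results from the clinical team. It does not. It limits return for treatment or follow-up decisions and allows exceptions. This stands, and the point is worded accordingly.
- **Scope.** The sentence sits in the biobank section, whose specimen list covers biopsy and leftover tissue, unused cells and procurement material, not the blood drawn for clonality. A narrower reading is possible. But the sentence speaks of correlative results without limit, and section 7.5 calls clonality correlative, so the text needs reconciling either way.
- **General safety routes.** Section 9.1.1 counts an abnormal laboratory finding as an adverse event. Section 10.4 has team meetings discuss safety and sends their summaries to the DSMC. A dominant clone could travel by either route, but only after someone on the clinical team knows of it, and that is the missing step.
- **DSMC.** A reader might infer that the DSMC reviews the trial without vector-safety data. The documents do not support that: reporting is neither barred nor required.
- **RCR and HAMA.** A reader might extend the gap to these. Both follow a clinical event, and for a delayed product-related event section 7.4 arguably already describes the use of results.
- **Risk.** Section 8.3 treats the stem-cell gene-therapy leukemias as likely special cases and reports that T cells carrying a related receptor expanded for only 2 to 3 weeks before declining. Few subjects may exceed 0.5% at month 6. That lowers the likelihood of the problem; it does not supply a route.
- **Unseen documents.** The Laboratory Manual, operating procedures and IRB approvals are not available here and may name a recipient. Because the exception requires the protocol itself to describe the use, a route held only elsewhere would not satisfy it.

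**Conclusion.** The point holds for clonality and integrant locus. Read literally, section 7.5.8 prevents a clonality result from informing follow-up in a subject without an adverse event, and no supplied passage says who is told, or what result would count as reportable. This is more than missing detail, because a stated rule works against the use of a scheduled safety test.

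Its size is one assay, in treated subjects above 0.5% transgene at month 6, for as long as testing continues. The documents give neither the share of subjects above that level nor a rate of dominant clones, so no expected number can be given. Counting scheduled samples would measure laboratory workload, not subjects at risk, especially since later annual samples may simply be archived (section 7.4).

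The conclusion assumes that the section 7.5.8 sentence applies to every test that section 7.5 calls correlative, and it is limited to the supplied text. It is a change worth making, not a flaw in the dose-finding design or its analysis.

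**What to change.** Reconcile sections 7.5.3 and 7.5.8 by adding one paragraph to 7.5.8 with this content:

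- The restriction does not apply to clonality and integrant-locus results (7.5.3), including integration-site findings from 7.5.5 that bear on clonality. For consistency, it also does not apply to event-triggered RCR results (7.5.2).
- The laboratory reports these results by study number to the Principal Investigator and the sponsor when they become available.
- The sponsor defines beforehand what counts as a reportable clonality result.
- The results are listed in the safety data sent to the DSMC under section 10.4.
- Any clinical action remains with the investigator.

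The restriction can stay for the other exploratory assays, and HAMA needs no place in this paragraph. The cost is an amendment with IRB approval and the sponsor's work on the definition. No test or sample is added. The clinical team would see some laboratory results, which is a small downside in an open-label, single-arm trial where there is no blind to protect.

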7.6 Patient Reported Outcomes Measures

Patient reported outcome measures will be collected on adult study participants who agree to fill out questionnaires at the scheduled clinic visits. The PROMIS questionnaires corresponding to Global Health (PROMIS GHS SF v1.0-1.1) and Physical Function (PROMIS Physical Function SF20a) (www.nihpromis.org) and selected symptom questions from the NCI PRO-CTCAE will be administered (see APPENDIX V - Patient Reported Outcomes Surveys).

Adult subjects who experience disease progression following an initial or subsequent cell infusion may be asked to complete a final set of questionnaires if they are willing.

Confidential

